6.5.4.2. Permanent Discontinuation of Study Medication

A patient's investigational product may be discontinued at any time at the patient's/parent's/legal guardian's request or at the discretion of the Investigator, the Medical Monitor, or the Sponsor. Justifiable reasons for the Investigator or the Sponsor to discontinue a patient from treatment may include, but are not limited to:

- The patient experiences any AE, clinically significant laboratory abnormality, or intercurrent illness, or other medical condition that indicates to the Investigator that continuation on study medication is not in the best interest of the patient (adverse event).
- A significant protocol violation (ie, patient failed to meet entry criteria or did not comply with protocol requirements resulting in an unacceptable risk to the patient's health) (protocol deviation).
- Noncompliance with study medication (non-compliance with study drug).
- Patient or parent/legal guardian decision to stop study medication (withdrawal by parent/guardian).
- Investigator discretion (physician decision).
- The patient participates in another investigational study without the prior written authorization of the Sponsor or its designee (protocol deviation).
- The patient becomes pregnant (pregnancy); study medication must be discontinued immediately once the patient becomes aware of the pregnancy and the investigator must be notified of the pregnancy (pregnancy) (see also [Section 10.6](#), Pregnancy Reporting).
- The patient's concomitant PKAN maintenance medications/therapies are adjusted during the double-blind period (protocol deviation).
- Patient is lost to follow-up (lost to follow-up).

Decisions to prematurely discontinue patients from study medication should be reviewed by the Investigator, the Medical Monitor, and the Sponsor.

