9.7. Unscheduled Visits

If a patient requires an unscheduled visit, the following assessments (at a minimum) should be performed:

- Assessments related to the purpose of the unscheduled visit
- AEs
- Concomitant medications

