10. ADVERSE EVENT REPORTING

10.1. Adverse Event (AE)

An AE is any untoward medical occurrence associated with the use of the investigational product (active or placebo) in a clinical investigation patient, which does not necessarily have a causal relationship with the investigational product. An AE can, therefore, be any unfavorable and unintended sign (eg, an abnormal laboratory finding), symptom, or disease temporally associated with the use of an investigational product, whether or not considered related to the investigational product.

Adverse events may include:

- Symptoms described by the patient
- Clinically significant changes in the patient's physical examination or other signs observed by the Investigator or medical staff
- Test abnormalities (laboratory tests, ECG, X-rays, etc.) that reflect a change from Baseline and/or that may result in changes in administration of investigational product or in an alteration in medical care (diagnostic or therapeutic)
- Conditions present at Baseline that have either worsened or recurred following resolution

The patient will be evaluated for new AEs and the status of existing AEs at each study visit, including the screening period, or at any time contact is made with the patient outside of a scheduled visit. The Investigator may elicit symptoms using an open-ended question, followed by appropriate questions that clarify the patient's verbatim description of AEs or change in concomitant medications.

Of note, bitter taste of study medication will not be captured on the AE eCRF. Any symptoms caused by the taste of study medication (eg vomiting, gagging) must be reported as an AE.

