10.6. Pregnancy Reporting

Although not an AE in itself, exposure to the investigational product during pregnancy must be reported, therefore all pregnancies will be recorded on the AE eCRF. If the Investigator suspects that a pregnancy was the result of an interaction between the investigational product and the contraceptive method, in addition to the pregnancy, the drug interaction should also be captured as a separate AE.

The Investigator will report any pregnancy associated with exposure to investigational product, including at least 30 days after final investigational product administration. When a site becomes aware that a patient or a male patient's partner is pregnant, they are to contact the Medical Monitor within 24 hours of the site staff becoming aware of the event, as well as complete an initial Pregnancy Notification Form and send by email it to the SAE contact on the [Study Contact Information](#) page of this protocol or by fax to the number in the study manual.

Female patients will be instructed to notify the Investigator and to stop taking study medication immediately if they discover they are pregnant. Male patients will be instructed to notify the Investigator immediately if they discover that their sexual partner is pregnant. In the latter instance, the partner must provide written consent before pregnancy information can be collected.

All pregnancies will be followed to outcome (ie, delivery, elective termination, spontaneous abortion). The Investigator will inform the patient that the Sponsor or its designee is required to gather information regarding the course and outcome of the pregnancy after exposure to the investigational product. All study related visits/contacts involving a known pregnancy should include pregnancy status assessment until pregnancy outcome is known. The Investigator should further obtain follow-up information no later than 1 month after the gestational period to obtain maternal/fetal/neonatal outcome and any other relevant information.

All information related to the pregnancy and its outcome will be assessed for the occurrence of an AE or SAE. Should an AE or SAE occur, it will be processed per study guidelines. Spontaneous abortions and stillbirths will always be reported as SAEs. If the pregnancy results in the birth of a child, and an AE/SAE occurs in the child, the data should be documented and, if

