Visit	V12	V13	V14	V15	V16	V17	V18	V19	V20	V21	V22- V28 ¹³	Unsched Visit ¹	End of Treatment/ Early Termination Visit/Final Contact ²
Study Week	W27 ± 7D	W30 ± 7D	W36 ± 7D	W48 ± 7D	W60 ± 7D	W72 ± 7D	W84 ± 7D	W96 ± 7D	W108 ± 7D	W120 ± 7D	W146, W172, W198, W224, W250, W276, W302 ± 7D		
Weight		X	X	X		X		X		X	X		X
Height (if <18 years of age at enrollment)		X				X				X	X		X
C-SSRS ³		X	X	X	X	X	X	X	X	X	X		X
Abbreviated physical examination ⁴		X	X	X		X		X		X	X		X
Vital signs ⁵	X	X	X	X	X	X	X	X	X	X	X		X
12-Lead electrocardiogram ⁵		X	X	X		X		X		X	X		X
Hematology ⁶	X	X	X	X		X		X		X	X		X
Chemistry ⁶	X	X	X	X		X		X		X	X		X
Coagulation ⁶		X								X	X		X
Urinalysis ⁶		X	X	X		X		X		X	X		X
Urine pregnancy ⁷		X*	X*	X*		X							
PKAN-ADL		X	X	X	X	X	X	X	X	X	X		X
UPDRS Part III		X	X	X	X	X	X	X	X	X	X		X
BAD scale				X		X		X		X	X		X
CGI-I		X	X	X	X	X	X	X	X	X	X		X
25-foot walk test ⁸			X	X		X		X		X	X		X
Neuro-QoL Adult/Pediatric (upper and lower extremity) ⁹			X	X		X		X		X	X		X
EQ-5D-3L/EQ-5D-Y ⁹				X		X		X		X	X		X
FIM/WeeFIM ⁹				X		X		X		X	X		X

Visit	V12	V13	V14	V15	V16	V17	V18	V19	V20	V21	V22- V28 ¹³	Unsched Visit ¹	End of Treatment/ Early Termination Visit/Final Contact ²
Study Week	W27 ± 7D	W30 ± 7D	W36 ± 7D	W48 ± 7D	W60 ± 7D	W72 ± 7D	W84 ± 7D	W96 ± 7D	W108 ± 7D	W120 ± 7D	W146, W172, W198, W224, W250, W276, W302 ± 7D		
Diadochokinetic Assessments ¹⁰				X		X		X		X	X		X
Pharmacokinetic sampling ¹¹		X											
Blood sample collection ¹⁴	At Selected Sites Only: 1 Blood sample ¹⁵												
Investigational product dispensing/accountability		X	X	X	X	X	X	X	X	X ¹²	X ¹²		X ¹²
AE Assessment	Continuous Monitoring												▶
Conmeds/therapies	Continuous Monitoring												▶

Abbreviations: AE = adverse event; BAD = Barry Albright Dystonia; CGI-I = Clinician Global Impression of Improvement; Con meds = concomitant medications; C-SSRS = Columbia Suicide Severity Rating Scale; D = Day; EQ-5D-3L/ EQ-5D-Y = EuroQol 5-dimension, 3-level quality of life instrument/EuroQol-5D Youth Version; FIM/WeeFIM = Functional Independence Measure/Functional Independence Measure for Children; Neuro-QoL = quality of life measure for adults/children with neurological disorders; PK = pharmacokinetic; PKAN-ADL = Pantothenate Kinase-associated Neurodegeneration Activities of Daily Living; Unsched = unscheduled UPDRS = Unified Parkinson’s Disease Rating Scale; V = Visit; W = Week

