¹ If a patient requires an unscheduled visit, assessments related to the purpose of the visit should be performed (see [Section 9.7](#)).

² For patients who are prematurely withdrawn from treatment (End of Treatment) or from the study (Early Termination) during the open-label period. If a patient who has prematurely discontinued study medication, decides to withdraw consent/assent and discontinue from the study within 6 weeks of completing the End of Treatment Visit, the End of Treatment Visit conducted at the time of study medication withdrawal may serve as the patient’s final site visit. If the study withdrawal occurs within 30 days of the patient’s last dose of investigational product, the patient will be contacted (via telephone call) 30 days (±7 days) after the last dose of investigational product to ascertain patient safety. Patients who complete the study will be contacted (via telephone call) 30 days (±7 days) after the last dose of investigational product to ascertain patient safety.

³ See [Section 9.3.5](#).

⁴ See [Section 9.3.1](#) for abbreviated physical examination assessments.

⁵ Vital signs and 12-lead electrocardiograms will be assessed 2 hours (± 30 minutes) after the first dose of the day at all visits. See [Section 9.3.2](#) and [Section 9.3.4](#). (Patients who have a DBS may experience interference with the ECG machine resulting in an inaccurate readout. In the best interest of the patient, the DBS device should not be turned off in an effort to collect the ECG, rather, using clinical judgement and following consultation with the Sponsor Medical Monitor, ECG assessments may be waived for these patients.)

- ⁶ Clinical laboratory parameters to be measured are listed in [Section 15.2.2](#). Laboratory assessments for coagulation factors to be collected once yearly during the open-label extension period.
- ⁷ To be assessed in women of childbearing potential only. Any positive urine pregnancy results will be confirmed by a serum pregnancy test. (*Norway and Poland specific procedure: Sexually active women of childbearing potential to conduct pregnancy testing at home between study visits. Site will provide the patient enough tests to conduct pregnancy testing once per month until the next scheduled study visit. A positive urine pregnancy test will be confirmed by a serum test).
- ⁸ See [Section 9.5.6](#).
- ⁹ See [Sections 9.5.4](#) and [Section 9.5.5](#) for age-based administration guidelines.
- ¹⁰ See [Section 9.5.6](#).

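### Open-label schedule: the urine pregnancy row goes blank after Week 72, leaving no test at nine later visits where urine is already collected or at End of Treatment/Early Termination

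*Protocol*

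**What the plan says.** **Schedule.** Protocol Section 15.1, Table 15.1-2, has a row labelled "Urine pregnancy". As extracted, it carries a mark with an asterisk at Weeks 30, 36 and 48 and a plain mark at Week 72. Every other cell is blank, including the combined Week 146 to 302 column and End of Treatment/Early Termination. In Table 15.1-1 (double-blind), the same test is marked at Baseline, Week 12, Week 24 and End of Treatment/Early Termination.

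**Footnote 7 to Table 15.1-2.** The general rule is "To be assessed in women of childbearing potential only. Any positive urine pregnancy results will be confirmed by a serum pregnancy test". The asterisk refers to an addition for sexually active women of childbearing potential in Norway and Poland, who test at home between visits: "Site will provide the patient enough tests to conduct pregnancy testing once per month until the next scheduled study visit". The footnote names no visit weeks and gives no end date.

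**Related rules.** Inclusion criterion 5 (Section 7.1) requires contraception for the whole study and at least 30 days after the last dose, in women of childbearing potential who are sexually active with male partners. It ties childbearing potential to being post-menarchal. Section 6.5.4.2 lists pregnancy as a reason to stop drug: "The patient becomes pregnant (pregnancy); study medication must be discontinued immediately once the patient becomes aware of the pregnancy". Section 10.6 covers reporting and follow-up once a pregnancy is known.

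**The concern.** The stop rule and the reporting duty both start from awareness: the patient's in Section 6.5.4.2, the site's in Section 10.6 ("When a site becomes aware that a patient"). A scheduled test creates awareness when nobody has noticed anything. The protocol uses one through Week 72 and gives no reason for ending it there, although drug is still dispensed at ten later visits (Weeks 84, 96, 108, 120, 146, 172, 198, 224, 250 and 276). Sections 9.3.5 and 13.4.1 also recognise that some patients are non-verbal or cognitively impaired, so relying on self-report is weaker here than in many trials.

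What is at stake is how long a fetus might be exposed to study drug before the drug is stopped. This is a patient-safety matter only.

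**Working it through.** The plan states no figure to reproduce, so the check is a count of visits and marks.

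**Inputs.** Open-label visits (Section 6.2): Weeks 27, 30, 36, 48, 60, 72, 84, 96, 108 and 120 (10 visits), then 146, 172, 198, 224, 250, 276 and 302 (7 visits), total 17. Marks come from Table 15.1-2:

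| Column | Urinalysis | Urine pregnancy |
|---|---|---|
| W27 | – | – |
| W30 | X | X* |
| W36 | X | X* |
| W48 | X | X* |
| W60 | – | – |
| W72 | X | X |
| W84 | – | – |
| W96 | X | – |
| W108 | – | – |
| W120 | X | – |
| W146–W302 (7 visits) | X | – |
| Unscheduled | – | – |
| End of Treatment/Early Termination | X | – |

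**Is the row misaligned?** It splits into 13 cells for 13 columns, as do the haematology and urinalysis rows. Of the 22 rows with per-visit marks, 20 keep their marks in both the Week 146 to 302 column and End of Treatment/Early Termination. The exceptions are this row and PK sampling, which is marked at Week 30 only. The late columns were therefore not lost in general.

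**Visits missing a test.** Urinalysis is marked at 4 visits through Week 72 and at 2 + 7 = 9 later visits, 13 in all. The pregnancy test is marked at 4 of the 13 and blank at 9. The End of Treatment/Early Termination cell is blank as well.

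**Time without a scheduled test.** 302 − 72 = 230 weeks. The open-label period is 302 − 24 = 278 weeks, and 230/278 = 83%.

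**After the fix.** Test intervals from Week 72 would be 24 and 24 weeks, then seven of 26 weeks: 48 + 182 = 230. The longest planned interval is 26 weeks, or 28 if one visit falls 7 days early and the next 7 days late. If a pregnancy begins at a uniformly random time between Weeks 72 and 302 in a woman who stays on study, the mean wait to the next scheduled test is

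ΣL² / (2ΣL) = (2 × 24² + 7 × 26²) / (2 × 230) = (1152 + 4732) / 460 = 5884 / 460 = 12.8 weeks,

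ignoring the short time before a urine test turns positive. Under the schedule as extracted there is no next scheduled test after Week 72, so no matching figure exists.

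**The case against.** **The blanks may be an extraction artefact.** This is the strongest objection. The row tracks urinalysis to Week 72 and then loses everything, and it is the only recurring assessment that stops. A simple failure to update the row when the extension was lengthened fits poorly. Section 6.5.4.2 still refers to visits through Week 120, which suggests (an inference) that Week 120 was once the last visit; an oversight of that kind would leave Weeks 96 and 120 marked. Correct column alignment does not rule out marks lost within this row. The objection stands as a reason to check the page first.

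**Other safeguards exist.** This also stands. Adverse events are asked about at each visit and "at any time contact is made with the patient outside of a scheduled visit", calls fall between the six-monthly visits after Week 120, and "all pregnancies will be recorded on the AE eCRF". An unscheduled visit includes "Assessments related to the purpose of the unscheduled visit", which could be a pregnancy test. Sites must contact the Medical Monitor within 24 hours of learning of a pregnancy. Section 9.1 points to study manuals that may say more and are not available here. A reader might infer that pregnancies after Week 72 would go undetected; the documents do not support that. What is missing is a scheduled test.

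**The frequency is a preference.** No rule sets a required frequency, so nothing here contradicts another provision. Even Table 15.1-1 does not pair the test with every urinalysis: of Weeks 3, 6, 12, 18 and 24, it marks the pregnancy test only at 12 and 24. The pairing is the open-label table's own pattern to Week 72. The case for extending it rests on continued dosing and the absence of any stated reason to stop.

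**Two further stronger readings fail.** One is that all 11 visits after Week 72 lack a due test. Weeks 84 and 108 have no urinalysis, just as Weeks 27 and 60 have neither assessment, so on the table's pattern the number is nine. The other is that girls who reach menarche on study are left out. Footnote 7 already covers anyone who becomes of childbearing potential under the post-menarchal definition.

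**Conclusion.** The point holds for the table as extracted: nine later visits with urine collection, plus End of Treatment/Early Termination, carry no pregnancy test, and the last 230 of 278 open-label weeks have none scheduled. It depends on the source page showing the same blanks, and on the study manuals not filling the gap.

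The benefit of closing it is modest. The 12.8-week mean wait describes the proposed schedule only, under an assumed uniform onset, and many women would notice sooner. The documents do not give the number of women affected. For Norway and Poland, the last asterisk is at Week 48 and the footnote has no end date, so whether home testing continues is unclear; the text does not establish that it stops. A reader might look for a consequence for the trial's conclusions. There is none: the open-label test schedule does not enter the 24-week efficacy comparison, its power or its type I error.

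**What to change.** 1. Check the urine pregnancy row on the source page of Table 15.1-2. If the later marks are there, nothing further is needed on the visit schedule.
2. If it is blank, mark the test at Weeks 96, 120, 146, 172, 198, 224, 250, 276 and 302 and at End of Treatment/Early Termination, for women of childbearing potential as already defined.
3. State in footnote 7 whether monthly home testing in Norway and Poland continues after Week 48, and until when.

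**Cost.** Up to about ten urine kits per eligible woman: nine visits, plus one at End of Treatment for a woman who stops drug but keeps attending visits. Add any home kits in the two countries. An amendment needs investigator signature and IRB/IEC approval (Section 13.3) at approximately 20 sites. No extra visit is needed, because urinalysis is already marked at each of these points.

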15.2.1. Allowed PKAN Maintenance Treatments

The PKAN maintenance treatments listed below are allowed during the study; however, dosage changes or adjustments including DBS can only be made during the double-blind period of the study following consultation between the Investigator, the Medical Monitor, and the Sponsor (except in cases of medical emergency such as dystonic crisis). Based on the Investigator's judgment, concomitant medications (excluding deferiprone) may be administered or modified at any time during the course of the study to treat AEs, symptoms, or disease states unrelated to managing the symptoms of PKAN.

Trihexyfenidyl

Benzodiazepines

Anticholinergics

Pain medications

L-dopa

Other treatments for Parkinsonism

Antipsychotics

Antidepressants

Treatments for attention deficit/hyperactivity disorder

Baclofen (oral or intrathecal pump)

Deep brain stimulation (DBS; if implanted \geq 6 months before screening, modifications to the settings are allowed; however, patients are not allowed to have a DBS implanted during the course of the study [double-blind and open-label])

Botulinum toxin; most recent injection must have occurred between 1 to 2 months prior to Baseline, and injections will continue on a regular schedule throughout the double-blind period.

15.2.2. Study Blood Assessments

Clinical Chemistry Sodium Potassium Chloride Bicarbonate Total protein Albumin Calcium Phosphate Glucose Blood Urea Nitrogen Creatinine Total bilirubin Alanine aminotransferase Aspartate aminotransferase Gamma-glutamyl transferase Lactate dehydrogenase Alkaline phosphatase Creatine kinase Total cholesterol Triglycerides
	
Hematology Red blood cell count Hemoglobin Hematocrit MCV, MCH, MCHC RBC distribution width Platelet count White blood cell count WBC Differential (% and absolute) 
 • Neutrophils • Eosinophils • Basophils • Lymphocytes • Monocytes 
	
Routine Urinalysis Color Appearance pH Specific gravity Protein Glucose Ketones Bilirubin Blood Urobilinogen Nitrates Leukocyte esterase Microscopic examination (performed if blood, protein, or leukocyte esterase is abnormal in urine)

Serology/Screening Tests Hepatitis B surface antigen Hepatitis C antibody HIV antibody Serum/Urine Pregnancy test Drug/Alcohol screen
	
Coagulation Prothrombin Time, INR aPTT
	
Potential Biomarkers^a Succinate Lactate Maleate Pyruvate Alanine Acetone Acetoacetic acid 3-hydroxybutyric acid 2-hydroxybutyric acid AcetylCoA

Abbreviations: aPTT= activated partial thromboplastin time; HIV=human immunodeficiency virus; INR=International Normalized Ratio; MCH=mean corpuscular hemoglobin; MCHC=mean corpuscular hemoglobin concentration; MCV=mean corpuscular volume; RBC=red blood cell; WBC=white blood cells
 
^a Additional potential biomarkers may be assessed, but the samples will not be used for genetic testing.
		

Signature Page for VV-CLIN-001743 v1.0

Approval	PPD 29-May-2019 02:02:48 GMT+0000
----------	--------------------------------------

Approval	PPD 29-May-2019 03:30:02 GMT+0000
----------	--------------------------------------

Approval	PPD 30-May-2019 02:43:57 GMT+0000
----------	--------------------------------------

Approval	PPD 30-May-2019 23:26:28 GMT+0000
----------	--------------------------------------

Signature Page for VV-CLIN-001743 v1.0

6.2.4	Prior and Concomitant Medications.....	46
6.2.5	Adverse Events	47

List of Abbreviations

AE	Adverse Event
AEOI	Adverse Event of Interest
AMR	Alternating Motion Rate
ANCOVA	Analysis of Covariance
ATC	Anatomical Therapeutic Chemical
BAD	Barry Albright Dystonia
BMI	Body Mass Index
BSA	Body Surface Area
CGI-I	Clinician Global Impression of Improvement
CI	Confidence Interval
CSR	Clinical Study Report
C-SSRS	Columbia- Suicide Severity Rating Scale
DDK	Diadochokinetic(s)
eCRF	Electronic Case Report Form
DMC	Data Monitoring Committee
ECG	Electrocardiogram
EQ-5D-3L	EuroQol 5-dimension, 3-level quality of life instrument
EQ-5D-Y	EuroQol-5D Youth Version
EU	European Union
FAS	Full Analysis Set
FIM	Functional Independence Measure
GLM	General Linear Model
ICF	Informed Consent Form
ICH	International Council for Harmonisation
INR	international normalized ratio
ITT	Intent-to-Treat
IWRS	Interactive Web Response System
KM	Kaplan-Meier
LOCF	Last Observation Carry Forward
LSM	Least-Squares Mean
MAR	Missing at Random
max	Maximum
MCAR	Missing Completely at Random
MCMC	Markov Chain Monte Carlo
MedDRA	Medical Dictionary for Regulatory Activities
min	Minimum
MMRM	Mixed Model for Repeated Measures
MNAR	Missing Not at Random
Neuro-	Quality of life measure for adults/children with neurological disorders

QoL	
OL	Open Label
PK	Pharmacokinetic(s)
PKAN	Pantothenate Kinase Associated Neurodegeneration
PKAN-ADL	Pantothenate Kinase Associated Neurodegeneration Activities of Daily Living Scale
PT	Preferred Term
REML	Restricted maximum likelihood
SAE	Serious Adverse Event
SAP	Statistical Analysis Plan
SD	Standard Deviation
SE	Standard Error
SMR	Sequential Motion Rate
SOC	System Organ Class
SUSAR	Suspected Unexpected Serious Adverse Reaction
TEAE	Treatment-Emergent AE
TID	ter in die (three times a day)
TLFs	Tables, Listings and Figures
UPDRS	Unified Parkinson's Disease Rating Scale
US	United States
WeeFIM	Functional Independence Measure for Children
WHO	World Health Organization

1 Introduction

This document summarizes key elements of the statistical analysis plan (SAP) for Protocol 024PKAN15004. The main purpose of this document is to describe the statistical methods to be used for the primary analysis of efficacy and safety endpoints collected during the double-blind portion of the study in support of an interim Clinical Study Report (CSR) for submission to regulatory authorities. This SAP also specifies the scope of analysis for available data collected in the open label portion of the study at the time of the database cut-off for the interim CSR. The plan for analysis of pharmacokinetics (PK) and pharmacogenomics data collected during this study is outside the scope of this SAP.

The SAP is being written in consideration of recommendations outlined in the International Council for Harmonisation (ICH) E9¹ Guideline entitled “Guidance for Industry: Statistical Principles for Clinical Trials” and the most recent ICH E3² Guideline, entitled “Guidance for Industry: Structure and Content of Clinical Study Reports.”

This SAP is based upon the following study documents:

- [Study Protocol, Version 3.0](#) (February 6, 2019)
- electronic Case Report Form (eCRF), Version 9.0 (March 4, 2019)

2 Study Objectives and Endpoints

The primary objective of this study is to evaluate the efficacy of fosmetpantotenate over 24 weeks in patients with Pantothenate Kinase Associated Neurodegeneration (PKAN).

The secondary objective is to assess the safety and tolerability of fosmetpantotenate in patients with PKAN.

Other objectives are:

- To determine the pharmacokinetics (PK) following multiple doses of fosmetpantotenate in patients with PKAN
- To explore biomarkers of disease, along with their potential response to treatment in patients with PKAN

